The purpose of this study is to investigate the usefulness of infusing purified CD34+ cells of donor origin in order to augment graft function in response to declining chimerism after initially performing an allogeneic hematopoietic stem cell transplant (HSCT) for children with primary immunodeficiency diseases. This protocol will be utilized for patients with waning mixed donor chimerism that is inadequate for correction of clinical condition or disease for which stem cell transplant was performed, or for augmentation of immune function. An infusion of selected CD34+ stem cells will be given without any preparative regimen. As the children eligible for this protocol have reduced immune function and pre-existing donor chimerism, we hypothesize that stem cells will be able to engraft and the infusion will augment graft function. This therapy serves as an alternative to a second stem cell transplant that is known to be associated with significant morbidity and mortality. CD34+ stem cells will be collected from the donor used for initial stem cell transplant. Cells will be T-cell depleted (TCD) by performing a CD34 selection using the CliniMACS device (Miltenyi Biotec) in order to prevent development of new or exacerbation of existing graft versus host disease (GVHD), as avoidance of GVHD in nonmalignant diseases is desirable. There is sufficient data showing that mixed donor chimerism is adequate for reverting disease phenotype in certain primary immunodeficiencies. Observations from Europe and CCHMC show that donor chimerism might be boosted by CD34+ stem cell infusion alone without any specific preparative regimen. This therapy is likely to be associated with low toxicity due to the absence of a preparative regimen and lack of exposure to fresh donor cells capable of initiating GVHD, and offers potential significant benefit.

I. PURPOSE OF STUDY

Hypothesis

Mixed or full donor chimerism that is adequate for disease control will be achieved with selected CD34+ stem cell infusion without preparative regimen with minimal or no therapy related toxicity or GVHD.

Objectives

- 1. Assess the toxicity of infusion of donor stem cells in augmentation of graft function in previously transplanted children with immune deficiencies, and bone marrow failures.
- Assess the efficacy of infusion of donor stem cells in augmentation of graft function in previously transplanted children with immune deficiencies, and bone marrow failures.

Endpoints

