The primary endpoint of the study is augmentation of graft function. Graft function will be measured in two ways. Firstly the percentage of donor chimerism, and secondly measured improvement in immune function; improvement in numbers of circulating white blood cells and/or platelets, and/or clearance of opportunistic viral infections.

 Improvement in immune function studies compared to baseline levels can be documented at 3, 6, and 12 months. Immune function studies will include quantitation of T and B cells and functional studies (mitogens and immunoglobulin levels). In the case of Wiskott-Aldrich syndrome, improvement of platelet count to >20,000/L on 2 separate occasions at least three months apart will be considered successful graft augmentation. Children requiring graft augmentation for a specific limited immune defect, e.g. inability to clear papilloma virus will also be assessed by clinical response of the infection; resolution or >50% improvement in infection will be considered successful graft augmentation.

The secondary endpoint is to determine the frequency and characteristics of potential infusion-related toxicity. Experience at our center, using CD34+ selected cells has shown infusion-related toxicity has occurred at an incidence of < 10% (zero toxicity in 9 patients participating in CCHMC IRB study # 2008-0777). While there is little expectation of infusion-related toxicity, the incidence of infusion-related reactions will be recorded and evaluated.

II. SIGNIFICANCE OF STUDY IN RELATION TO HUMAN HEALTH

Primary or congenital immunodeficiency diseases result from inborn genetic defects of the immune system frequently manifesting itself as recurrent and chronic infections and

commonly lead to lethal complications. Currently, more than 100 immunodeficiency diseases have been identified and classified according to the area of immune system that is compromised. Most of these have been molecularly defined and are due to single gene defects.

Allogeneic hematopoietic stem cell transplantation is the only curative approach to date for most of the lethal immunodeficiency diseases including severe combined immunodeficiencies (SCID), T-cell immunodeficiencies, Wiskott-Aldrich syndrome, Chediak-Higashi syndrome and others, where it restores immune function and decreases risk of long term complications such as malignant transformation.

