• Debilitating secondary disease known to be a consequence of inadequate immune response to known agent or pathogen, uncontrollable by other available medical therapies (e.g. third patient described on page 5).

2b. Exclusion Criteria

- 1. Absence of an available original donor
- 2. Failure to sign consent form, or inability to undergo informed consent process
- 3. Pregnant or lactating female
- 4. Uncontrolled GVHD

3. **Randomization**

Not applicable.

4. **Procedures**

Pre-infusion evaluation:

Patients enrolled on this protocol will be evaluated for disease status and organ function prior to stem cell infusion, required testing as follows:

- 1. Peripheral Donor Chimerism Studies
- 2. CBC with differential and platelets
- Immunological studies including but not limited to absolute numbers of all lymphocyte subsets NK, T, B lymphocyte function, proliferation to mitogens, immunoglobulins
- 4. Urine pregnancy tests for girls of childbearing age
- 5. Renal and liver function tests

Treatment Plan:

Treatment Scheme

This treatment will involve these steps:

- 1. Pre-infusion evaluation
- 2. Collection of Granulocyte Colony Stimulating Factor (GCSF) mobilized peripheral blood stem cells from same donor used for first transplant as per standard procedures
- 3. Selection of CD34+ stem cells and T-cell depletion using CliniMACS
- 4. Infusion of stem cells into recipient
- 5. Continue monitoring

Schedule*:

Pre-infusion	Clinic visit and evaluation of peripheral blood counts	
Day 0	Infusion of CD34+ selected stem cells	
Day 7	Clinical assessment	
3, 6, 12	Clinical assessment	
months and	Donor chimerism studies	
then yearly for	Immunological studies	
up to 3 years		
post infusion		

*For details see Required Observations, page 10.

Additional testing such as disease specific markers (CD132, WASP) or more frequent testing might be needed at attending physician discretion if indicated by patient's clinical condition.

Preparative therapy:

No preparative therapy or additional immunosuppressive therapy will be given in preparation to stem cell infusion.

Stem Cell Infusion:

Stem Cells will be administered per standard institutional protocols.

Immune Suppression after stem cell infusion:

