Viable CD3+/Kg	Flow Cytometry	≤ 5 x 10⁴/kg
Gram Stain	Gram Stain	Negative

Safety of Product

Unrelated donor evaluation will be completed per the relevant unrelated donor registry standards (additional testing at discretion of physician and NMDP/registry donor center).

Related donors will be evaluated per donor standard operating procedures. As part of this research we will collect clinical data to ensure eligibility.

Product testing

The following tests will be performed on each product produced to assure product safety, purity, and potency:

Pre CD34 Selection (T cell Depletion): Total nucleated cell count Viability CD 34+ cells/kg of recipient CD 3+ cells/kg total volume collected sterility (bacterial and fungal culture)

Post CD34 Selection (T cell Depletion): Total nucleated cell count Viability Viable CD 34+ cells/kg of recipient Viable CD 3+ cells/kg of recipient total volume for infusion endotoxin assay (Limulus Amebocyte Lysate Test or equivalent) stat gram stain sterility (bacterial and fungal culture)

Culture of the product:

If the culture of the product (either fungal or bacterial) becomes positive following infusion of the cells, antibiotics or antifungal medications will be administered to the recipient. The patient/guardian and treating physician will be informed.

Endotoxin testing:

An endotoxin assay will be performed on the post-selection product within 24 hrs of infusion, and the patient's physician will be notified if more than 5 EU/kg was infused into the recipient.

Required Observations:

1. Clinical Assessment

An assessment of the patient will be done on Day 7 (+/- one day), at three months (+/- four weeks), and at or around six and twelve months. This will include a complete physical exam and CBC.

2. Donor chimerism studies

Peripheral blood donor chimerism studies will be performed only for subjects for whom the CD34 product has been provided for inadequate donor chimerism. Chimerism studies will be performed at or around three, six and twelve months, then annually for up to 3 years after the stem cell infusion. Thereafter, chimerism studies will be performed as clinically indicated. Donor chimerism analysis will be done on peripheral blood using standard FISH or VNTR analysis.

3. Immunological studies

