Appropriate immunologic studies relevant to indications for CD34 infusion will be performed for stratum II and stratum III patients (see strata on page 6) at three months (+/- four weeks) and at or around six, twelve months and annually for up to 3 years post infusion. These tests will include, but not be limited to, lymphocyte subsets, T cell activation and NK function.

Additional testing like disease specific markers (CD132, WASP) or more frequent testing might be needed at attending physician discretion if indicated by patient's clinical condition.

5. Blood Specimens

Not applicable

6. Other Previously Approved Research Studies In Which The Projected Patient Population May Also Be Involved (include what precautions will be taken to avoid any cumulative risk, e.g., repeated blood sampling, radiation exposure, etc.)

Patients eligible for this study may beeligible for other open therapeutic studies at CCHMC. Study options will be discussed and decided on a case-by-case basis.

7. Data Analysis/Statistical Considerations

Primary Endpoints

The primary endpoint of the study is augmentation of graft function. Graft function will be measured in two ways: firstly the percentage of donor chimerism, and secondly immune function.

Successful augmentation of graft function will be achieved if:

- Donor chimerism is doubled compared to the value immediately pre-infusion at 3, 6, and 12 months, -OR-
- Improvement in immune function studies compared to baseline levels can be documented at 3, 6, and 12 months. Example of immune function studies which would be used would include quantitation of T and B cells and functional studies (mitogens and Immunoglobulin levels). In the case of Wiskott-Aldrich syndrome, improvement of platelet count to >20,000/L without transfusions on 2 separate occasions at least three months apart will be considered successful graft augmentation. Children requiring graft augmentation for a specific limited immune defect, e.g. inability to clear papilloma virus will also be assessed by

clinical response of the infection; resolution or >50% improvement in infection will be considered successful graft augmentation.

Secondary Endpoints

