Graft versus host disease (GVHD): GVHD is unlikely as a low number of T-cells will remain after cell selection and the recipients already have stable mixed chimerism with cells from their donors. Acute GVHD can cause a skin rash, liver dysfunction, and/or enteritis, and is potentially fatal. Chronic GVHD is a multi-organ autoimmune disease, which may resolve over several months or years or lead to death, commonly from infection.

2. Precautions that will be taken to monitor and avoid the above mentioned risks, discomforts, and inconveniences, including methods for detecting adverse events

Infusion reactions: The risk of transfusion reaction will be minimized by appropriate testing of the donor and products, and by use of pre-medication. Pre-medications will be given according to standard practice. Patients will be monitored according to CCHMC guidelines during stem cell infusion for any infusion reactions. To reduce the risk of product infusion, CD34+ stem cells will be highly T-cell depleted. Should an infusion reaction occur it will be treated with supportive therapy according to standard transplant procedure.

Graft versus host disease: The risk of developing a new case of GVHD is anticipated to be very low. No GVHD prophylaxis will be given. Any occurring

GVHD would be treated according to accepted standards.

3. The method of monitoring study conduct.

All grade 3 or greater adverse events occurring during this study will be recorded on the case report forms. The principal investigator will review each event and assess its relationship to study events as to whether the event is unrelated, unlikely related, possibly related, probably related, or definitely related to the study device. The CTCAE Version 3.0 will be used to evaluate these adverse events.

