This population of patients, by nature of their various disease/conditions and due to effects from the original allogeneic hematopoietic stem cell transplantation (with a full preparative regimen), often continue to experience disease and therapy-related complications and are frequently hospitalized for observation and/or treatment of these conditions. As these patients do not receive any preparative therapy as participants in this study, the risk of study-related toxicity is expected to be minimal. Consequently any serious adverse events, as defined by the IRB guidelines, that are determined to be possibly, probably or definitely related to the study device will be reported according to IRB reporting regulations. However, serious adverse events determined to be related to the patient's underlying disease/condition or to the first transplant procedure, including hospitalizations or prolongation of hospitalizations resulting from such events, will not require expedited reporting to the IRB. These events will be reported annually with the progress report. Please note that for the purpose of this study we will exclude the report of hematologic toxicities, as these subjects, by virtue of their underlying disease and/or condition may present with baseline hematologic toxicity.

Although these subjects will be followed on study for up to 3 years post infusion, all adverse events (as described above) will be captured for the first 30 days post stem cell infusion. Thereafter, only related adverse events will be recorded on case report forms.

4. Methods for maintaining data quality and confidentiality

Data quality is monitored and audited by the Center for International Blood and Marrow Transplant Research and the National Marrow Donor Program. Confidentiality is maintained as per section VI.

5. An assessment of accrual (timely enrollment) and the handling of dropouts.

Accrual assessment will be evaluated by the principal investigator with the annual progress review. Subjects who do not complete a full six months of follow up will not be counted in the total stratum accrual and will be replaced.

6. Risk assessment recommendation

- Minimal risk but with direct benefit to participants
- Minimal risk but without direct benefit to participants

More than minimal risk but with direct benefit to participants

More than minimal risk but without direct benefit to participant

7. Data and Safety Monitoring Plan

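### Section VI.3 excludes hematologic toxicities from reporting with no change-from-baseline rule, so new or worsened cytopenia can drop out of the adverse event frequency, and its place under the grade 4 suspension rule is unclear

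*Combined protocol and SAP*

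**What the plan says.** The first objective in section I is to "Assess the toxicity of infusion of donor stem cells in augmentation of graft function in previously transplanted children with immune deficiencies, and bone marrow failures". Under Statistical Analysis in the Data Analysis section, all 45 patients are pooled to estimate the frequency of adverse events, which is expected to be below 5%.

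Section VI.3 opens with a general rule: "All grade 3 or greater adverse events occurring during this study will be recorded on the case report forms". Its next paragraph, after describing expedited and annual reporting to the IRB, says that "for the purpose of this study we will exclude the report of hematologic toxicities". The reason given is that these subjects "by virtue of their underlying disease and/or condition may present with baseline hematologic toxicity". Section VI.3 then captures all adverse events for 30 days after infusion and only related events after that.

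Counts also appear on the benefit side. The Endpoints text in section I lists "improvement in numbers of circulating white blood cells and/or platelets" as part of graft function. The Data Analysis section makes "improvement of platelet count to >20,000/L without transfusions on 2 separate occasions at least three months apart" a success in Wiskott-Aldrich syndrome.

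The counts are measured in any case. The pre-infusion evaluation requires "CBC with differential and platelets". For the assessments at day 7 and at 3, 6 and 12 months, Required Observations says: "This will include a complete physical exam and CBC".

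**The concern.** The product acts on the blood-forming system, and the population includes bone marrow failure. The exclusion covers the organ system in which an unwanted effect would be of most interest.

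The stated reason does not reach as far as the rule. Abnormal counts at entry make absolute grades hard to interpret. That is a reason to grade against baseline, not to leave out the whole class. The text says only that subjects may have such abnormalities, and the inclusion criteria agree: thrombocytopenia is one of several alternative routes to entry, so a patient can enter with normal counts.

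At stake is the safety half of the hypothesis, which expects little or no treatment-related toxicity. If hematologic events are left out by rule, a low reported frequency would partly reflect the rule rather than the data. There is also no independent check: section VI.7 provides no DSMB or medical monitor, and the Stopping Rules let the IRB act on the serious events reported to it.

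**Working it through.** The plan states no figure on this point, so there is none to reproduce. The check is a reading of the rules against one another, with a short calculation for scale.

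**1. Breadth of the exclusion.** The sentence in section VI.3 has no qualifier for grade, change from baseline, time since infusion or attribution. Read literally, it covers an event judged definitely related to the infusion.

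**2. Which rule governs.**

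| Place | Rule | Hematologic exception? |
|---|---|---|
| VI.3, first paragraph | All grade 3 or greater events go on the case report form | None stated |
| VI.3, second paragraph | Hematologic toxicities are excluded from report | This is the exclusion |
| VI.3, capture window | All events, as described above, to day 30; related events afterwards | Unclear: it refers back to text that includes the exclusion |
| Stopping Rules | Any serious unexpected grade 4 event suspends enrollment | None stated |
| VI.7 | Any such event during infusion or within 30 days is reported expeditiously | None stated, but it points to VI.3 |

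Two readings are possible. On the broad one, hematologic events are not collected as adverse events and cannot enter the 45-patient frequency. On the narrow one, the exclusion concerns only reports to the IRB and the case report form still holds them. The text does not choose between the two.

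**3. Benefit against harm.** The success criteria in the Data Analysis section are alternatives. A patient whose donor chimerism doubles is a success whatever happens to the neutrophils or platelets. On the broad reading, a patient with doubled chimerism and a new grade 4 cytopenia is a success with no reported toxicity. A patient whose counts collapse and one whose counts do not change can both be plain non-responders.

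**4. What the scheduled counts can supply.** There is one baseline count and four follow-up counts (day 7, months 3, 6 and 12). Only day 7 falls in the 30-day all-event window. At months 3, 6 and 12 a new cytopenia would be an adverse event entry only if judged related, even without the exclusion.

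**5. Scale, for illustration.** Inputs: n = 45 and the 5% ceiling, both from Statistical Analysis. The other rates are assumptions. The chance of at least one event is 1 − (1 − p)^45:

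- p = 1%: 1 − 0.99^45 = 36.4%
- p = 2%: 1 − 0.98^45 = 59.7%
- p = 5%: 1 − 0.95^45 = 90.1%
- p = 10%: 1 − 0.90^45 = 99.1%

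In a stratum of 10 at 5% the figure is 1 − 0.95^10 = 40.1%, which agrees with the plan's reason for pooling. If no event were reported in 45 patients, the exact one-sided 95% upper limit would be 1 − 0.05^(1/45) = 6.4%. On the broad reading that limit says nothing about hematologic events.

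**The case against.** The strongest reply is that the exclusion is narrower than it looks. It follows directly on sentences about IRB reporting and speaks of the report, while the general rule that all grade 3 or greater events go on the case report form is left standing. This is a fair reading, and it rules out any flat claim that no hematologic event is captured. It does not settle the matter, because the capture sentence that follows refers back to the same text.

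A reader might infer that a grade 4 cytopenia can never trigger suspension. The documents do not support that: the Stopping Rules cover any serious unexpected grade 4 event and make no hematologic exception. What stands is that section VI.7 sends the reader to the section that holds the exclusion.

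A reader might also infer that graft loss is hidden by the rule. The exclusion does not name graft loss, and no text classes it as a hematologic toxicity. Where the infusion was given for inadequate chimerism, a fall in chimerism would fail the doubling criterion. Nor are the blood counts ignored for safety: under section VI.7 the principal investigator monitors safety and reviews all protocol-related laboratory results. The gap is in reporting and analysis, not in observation.

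Two further points limit the consequence. The formal secondary endpoint is infusion-related toxicity, described as shortness of breath, fever or anaphylaxis, which the exclusion hardly touches. And general recovery of white cells and platelets appears in the Endpoints text but is not among the success criteria in the Data Analysis section, which name T and B cell numbers and the Wiskott-Aldrich platelet threshold. The imbalance between benefit and harm is therefore partial.

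**Conclusion.** The concern holds in a limited form. The exclusion has no change-from-baseline, grade or attribution limit, and its reason applies only to some patients. New or worsened cytopenia, including cytopenia related to the infusion, can therefore drop out of the pooled adverse event frequency that serves the first objective, while some count gains can support efficacy. Separately, section VI.3, the Stopping Rules and section VI.7 conflict, so it is unclear whether hematologic events reach the suspension rule.

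The size cannot be stated from the documents, which give no hematologic event rate. The 36.4% to 99.1% range rests on assumed true rates of 1% to 10%. It shows only that such events could plausibly occur in 45 patients and, on the broad reading, not be counted. The documents do not support saying that these events never reach the suspension rule, that none are captured, that the counts play no part in safety, or that graft loss is excluded. The change should be made, since it removes a possible bias from the safety answer at little cost.

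**What to change.** Replace the exclusion in section VI.3 with wording such as:

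> Hematologic abnormalities present at baseline and not worsened after infusion are not reported as adverse events. New hematologic events of grade 3 or greater, and worsening from baseline to grade 3 or greater, graded by CTCAE version 3.0, are recorded within the capture window of this section: all events to day 30, related events thereafter.

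Add to Statistical Analysis a shift table of baseline grade against worst post-infusion grade for each count, from the scheduled CBCs (baseline, day 7, months 3, 6 and 12). The table needs no judgement of relatedness, so it also covers the visits after day 30. It should be read with the gap between day 7 and month 3 in mind, since a fall and recovery in that interval would not show.

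Reconcile section VI.3, the Stopping Rules and section VI.7 so that they say in the same terms whether hematologic events fall under the suspension rule. That choice is the sponsor's.

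The cost is a wording amendment, one table from blood counts already scheduled, and some extra event entries, some of which will reflect underlying disease rather than the infusion.

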Five patients will be enrolled into each stratum for evaluation of graft augmentation. If none of the five patients per stratum show any graft augmentation after one year, accrual to that particular stratum will be closed due to lack of efficacy. Patients will continue to be enrolled into other strata until criteria for five patients per stratum are fulfilled. If one out of five patients per stratum will meet listed criteria for graft augmentation, the next five patients may be enrolled to that stratum. If graft augmentation is seen in 1 of 5 or 2 of 10 cases in any stratum the strategy will be considered worthy of further investigation.

Since initiation of the study, it has been noted that stratum III encompasses a wide variety of diseases and therefore the majority of subjects enrolled have been to this stratum. As at least one subject has met the criteria for improved graft augmentation, the target enrollment for stratum III will be increased to 15 to accommodate this large group of patients.

If the infusion of purified CD34+ donor cells does not increase graft augmentation, patient will be removed from study and treated according to standard procedures.

There are no specific plans at this time to treat the patient with an additional boost of CD34+ cells if graft augmentation does not occur on study. However, this decision will be made on a per case basis as clinically indicated.

2a. Inclusion Criteria

To be eligible for this protocol, patients must have the following:

- 1. Primary immunodeficiency (e.g. SCID, Wiskott-Aldrich and/or other more rare conditions), or a bone marrow failure syndrome with prior allogeneic stem cell transplant.
- 2. Waning donor chimerism or immune function that is inadequate to correct their disease or clinical condition, for which primary transplant was given, as determined by their attending physician.
- 3. Available primary donor.
- 4. Must not have other organ dysfunction deemed by the attending physician to preclude this procedure.

- 5. Age < 35 years at time of transplant
- 6. One of the following must be true:
 - Patients must have evidence of persistent or recurrent immunodeficiency or thrombocytopenia.

-OR-

• Primary immunodeficiency disease with known potential to progress to malignant condition if untreated.

-OR-

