Infusional Toxicity: Infusion of stem cells could result in infusion reaction presenting as shortness of breath, fever, or anaphylaxis. To reduce the risk of infusion reaction, CD34+ stem cells will be highly T-cell depleted. While we have the expectation of a low occurrence of this toxicity, we will monitor for the frequency and characteristics of infusion related toxicities.

Statistical Analysis

We expect the frequency of adverse events in this study to be low (likely less than 5% events). We will therefore use all 45 patients to determine the frequency of adverse events as our ability to correctly define the frequency of events in any one stratum of 10 cases is low.

Descriptive statistics will be compiled on responding and non-responding cases, including patient and graft characteristics that might influence response. It is recognized that this portion of the analysis is exploratory due to the small sample size, but these data will be used to inform the design of future studies.

Stopping Rules

The primary endpoint of this study is qualitative graft augmentation. Five patients will be enrolled into each stratum for evaluation of graft augmentation. If none of the five patients per stratum show any graft augmentation, accrual to that particular stratum will be closed due to lack of efficacy. Patients will continue to be enrolled into other strata until criteria for five patients per stratum are fulfilled. If one out of five patients per stratum will meet listed criteria for graft augmentation, an additional five patients may be enrolled to that stratum.

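### Replacing every patient with under six months of follow-up can take infused early deaths and losses out of the stratum response counts, which favours success if non-responders are lost early at a higher rate than responders

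*Combined protocol and SAP*

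**What the plan says.** Section VI.5, on accrual and dropouts, gives the counting rule: "Subjects who do not complete a full six months of follow up will not be counted in the total stratum accrual and will be replaced". Neither the reason for the short follow-up nor receipt of the infusion matters.

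The efficacy decisions are in the enrolment plan just before 2a (Inclusion Criteria) and are partly repeated under Stopping Rules in Section 7.

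- **Closure:** the enrolment plan closes a stratum "If none of the five patients per stratum show any graft augmentation after one year". Stopping Rules repeats this without the one-year time point: "If none of the five patients per stratum show any graft augmentation, accrual to that particular stratum will be closed".
- **Expansion:** one response among five allows five more patients.
- **Positive conclusion:** "If graft augmentation is seen in 1 of 5 or 2 of 10 cases in any stratum", the approach is held to merit further study.

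Response is defined under Primary Endpoints in Section 7. The chimerism criterion reads "Donor chimerism is doubled compared to the value immediately pre-infusion at 3, 6, and 12 months", and the immune-function criterion names the same months. Two criteria are not tied to those months. One is the Wiskott-Aldrich platelet criterion, which needs two qualifying counts at least three months apart. The other is the infection criterion: "resolution or >50% improvement in infection will be considered successful graft augmentation".

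The enrolment plan adds that if the infusion "does not increase graft augmentation, patient will be removed from study and treated according to standard procedures". It gives no time for that removal.

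The Statistical Analysis text says "Descriptive statistics will be compiled on responding and non-responding cases", but not how a patient lost early is to be classified.

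**The concern.** A replaced patient's place is taken by another, so the five or ten patients judged in a stratum are those who stayed six months. An infused patient who dies in month 2 without a response is a failure of the strategy, yet would not appear in the count. Section VI.1 itself lists acute GVHD as potentially fatal, and Section VI.3 describes a population with frequent complications and hospital stays, so early losses are conceivable.

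These counts are the only efficacy decision rule visible in the plan, and a single response decides whether a stratum continues. A stratum could stay open, or be declared promising, on a count that leaves out infused patients who failed early. A reader of a reported 1 of 5 could not tell how many were infused. If two failures had been replaced, the result would be 1 of 7 infused, or 14.3%.

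**Working it through.** **Is there a plan figure to reproduce?** No. The text available gives no null or target response rate, error rate, power or dropout rate for the stratum rules. All rates below are assumptions.

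**Inputs from the plan:** the replacement rule (VI.5), and the thresholds 0 of 5, 1 of 5 and 2 of 10 (enrolment plan, Stopping Rules).

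**Assumed inputs:** p, the true response rate among all infused patients; q, the share of non-responders lost before month 6; r, the same share for responders.

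**Formulas**

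- Share of infused patients lost: p·r + (1−p)·q
- Response rate among counted patients: x = p(1−r) / [p(1−r) + (1−p)(1−q)]
- Reading A, at least 1 of 5: A = 1 − (1−x)^5
- Reading B, at least 1 of 5 and then at least 2 of 10 in total: B = P(at least 2 of 5) + P(exactly 1 of 5) × A

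**Example.** With p = 10%, q = 25%, r = 0: x = 0.10 / (0.10 + 0.90 × 0.75) = 0.10 / 0.775 = 12.9%. Then A = 1 − 0.871^5 = 49.9%. P(exactly 1 of 5) = 5 × 0.129 × 0.871^4 = 37.1%, so P(at least 2 of 5) = 49.9% − 37.1% = 12.8%, and B = 12.8% + 37.1% × 49.9% = 31.3%.

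| p | q | r | Infused lost | x | A | B |
|---|---|---|---|---|---|---|
| 10% | 0 | 0 | 0 | 10.0% | 41.0% | 21.6% |
| 10% | 10% | 0 | 9.0% | 11.0% | 44.1% | 24.9% |
| 10% | 25% | 0 | 22.5% | 12.9% | 49.9% | 31.3% |
| 10% | 25% | 10% | 23.5% | 11.8% | 46.5% | 27.5% |
| 10% | 25% | 25% | 25.0% | 10.0% | 41.0% | 21.6% |
| 10% | 10% | 20% | 11.0% | 9.0% | 37.6% | 18.3% |
| 20% | 0 | 0 | 0 | 20.0% | 67.2% | 53.8% |
| 20% | 10% | 0 | 8.0% | 21.7% | 70.6% | 58.7% |
| 20% | 25% | 0 | 20.0% | 25.0% | 76.3% | 66.9% |

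**What sets the direction.** x exceeds p exactly when q exceeds r. It is not enough that most losses are failures. In the row with q = 10% and r = 20%, failures make up 0.09 / 0.11 = 82% of the losses, yet the chance of success falls from 41.0% to 37.6%. At equal loss rates and p = 10%, 90% of losses are failures and nothing changes.

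**Can responders be lost before month 6?** Yes, on two criteria. Under Required Observations, blood counts are due at day 7 and at three months, give or take four weeks. Those two can be three months apart, so the platelet criterion could be met by about month 4. The infection criterion has no fixed month. For chimerism and immune function it depends on whether months 3, 6 and 12 are all required, which the text does not settle. If they are, nobody lost before month 6 can have met those two criteria.

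**The case against.** The strongest objection is that VI.5 speaks of accrual, under a heading about timely enrolment and dropouts, and does not mention response or an efficacy denominator. It might have been meant for voluntary dropouts, or for enrolled patients whose product failed release. The stratum definitions and the text just before the enrolment plan were not available for this check, and a rule on evaluable patients could stand there. This stands as a limit: the link to the decision counts is an inference. It is still the natural one, because the sentence is not restricted by reason and no other per-stratum count is visible.

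Second, early failures may be few. The plan expects little toxicity without a preparative regimen and calls GVHD unlikely. GVHD of grade II or above suspends the study for review, so such a case would not escape oversight. That is fair, but oversight of safety does not settle who is in the efficacy denominator.

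Third, a reader might infer that the removal statement sends non-responders out before month 6 and so deletes them systematically. The documents do not support that. No time is given, the more natural reading is removal after the one-year judgement, and a patient given a second transplant but still followed to month 6 is not replaced. On that reading the route is limited to early deaths, withdrawals and other losses.

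**Conclusion.** The point holds in a conditional form. As written, the replacement rule can remove infused early deaths and losses from the counts behind the 0-of-5, 1-of-5 and 2-of-10 decisions, provided that the accrual count is the efficacy denominator. The result tilts toward success only if non-responders are lost early at a higher rate than responders.

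A reader might infer that the rule is shown to inflate success, or that it does so whenever early losses are mostly failures. Neither follows. The documents give no loss rates, and the direction depends on the two rates, not on the make-up of the losses.

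Under the assumed rates with only non-responders lost, the chance of at least 1 of 5 rises by about 3 to 9 percentage points. On the two-stage reading the rise is about 3 to 13 points. That is modest, but in groups of five each omitted patient matters, and the repair is cheap. It should be fixed.

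**What to change.** Replace the sentence in VI.5 with:

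> Every patient who receives the CD34+ infusion counts in the stratum denominator, in order of infusion. An infused patient who dies or leaves follow-up before the one-year assessment without having met the response criteria counts as a non-responder; one who had already met them counts as a responder. Only enrolled patients who were never infused are replaced.

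The cut-off is one year rather than six months because the enrolment plan judges response at one year. The current text does not classify patients lost between months 6 and 12.

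In addition:

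- Report each stratum's count with and without any patients already replaced, with reasons.
- State that adverse event frequency is based on all infused patients. The Statistical Analysis text uses all 45, which is the accrual target, and does not say whether replaced patients are included. VI.3 already captures their events for 30 days.
- Reconcile the untimed removal statement with the one-year judgement.

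**Cost.** This needs a short amendment, and a listing and reclassification of any patients already replaced, since enrolment is under way. No extra patients are needed. A reported response rate may fall, and a stratum already extended may need its count restated.

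The statistical downside is that losses unrelated to response count as failures. With r now the share of would-be responders lost before meeting the criteria, P(0 of 5) = [1 − p(1−r)]^5. At an assumed p = 20% this is 0.80^5 = 32.8% with r = 0, 0.82^5 = 37.1% with r = 10%, and 0.84^5 = 41.8% with r = 20%. Showing both counts makes this visible.
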